Misdiagnosis caused by product's error	Incidence with SW System not > documented incidence with similar devices	Clinical	
 
- Incidents and adverse events (if any) related to the DUE and linked to misdiagnosis caused by product's error in the DUE do not result in serious harm, injury or impairment to the patient. 
 
o No serious clinical complications or other effects linked to misdiagnosis caused by product's error in the DUE are observed in the clinical studies and registries performed with the DUE.
 
 
 
- Incidents and adverse events (if any) related to the DUE and linked to misdiagnosis caused by product's error in the DUE do not frequently result in serious harm, injury or impairment to the patient. 
 
o Output from ongoing review of incidents and adverse events (if any) related to the DUE and similar devices confirms a low incidence of clinical complications or other effects linked to misdiagnosis caused by product's error.
 
 
 

	Incidence with SW System not > documented incidence with similar devices	Clinical	
 
- Incidents and adverse events (if any) related to the DUE and linked to misdiagnosis caused by user's error in the DUE do not result in serious harm, injury or impairment to the patient.
 

Dilemma Solutions S.L.	CHAPTER 06-1C	TD01-06-1C Ver.: 01 2025/03/03
	CLINICAL EVALUATION PLAN (CEP)	Page 28 of 38

Misdiagnosis caused by user's errors			
 
○ No serious clinical complications or other effects linked to misdiagnosis caused by user's error in the DUE are observed in the clinical studies and registries performed with the DUE.
 

			
 
- Incidents and adverse events (if any) related to the DUE and linked to misdiagnosis caused by user's error in the DUE do not frequently result in serious harm, injury or impairment to the patient. 
 
○ Output from ongoing review of incidents and adverse events (if any) related to the DUE and similar devices confirms a low incidence of clinical complications or other effects linked to misdiagnosis caused by user's error in these systems.
 
 
 

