Patient's privacy and data security	Incidence with SW System not > documented incidence with similar devices	Clinical	
 
- Incidents and adverse events (if any) related to the DUE and linked to patient's privacy and data security issues in the DUE do not result in serious harm, injury or impairment to the patient. 
 
○ No serious clinical complications or other effects linked to patient's privacy and data issues in the DUE are observed in the clinical studies and registries performed with the DUE.
 
 
 

			
 
- Incidents and adverse events (if any) related to the DUE and linked to patient's privacy and data security issues in the DUE do not result in serious harm, injury or impairment to the patient. 
 
○ Output from ongoing review of incidents and adverse events (if any) related to the DUE and similar devices confirms a low incidence of clinical complications or other effects linked to patient's privacy and data security issues in these systems.
 
 
 

Dilemma Solutions S.L.	CHAPTER 06-1C	TD01-06-1C Ver.: 01 2025/03/03
	CLINICAL EVALUATION PLAN (CEP)	Page 29 of 38

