## Overview

This is the first Clinical Evaluation Plan according to the Regulation (EU) 2017/745 on medical devices, since the DUE, NAEVIA MEDICAL, has not been on the market before (2017).

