Exclusion criteria	
 
- Subjects under 18 years of age.
 
- Inability to anonymise the case.
 
- Clinical cases of valvular heart disease involving complex congenital heart disease.
 
- Clinical cases that do not meet the minimum set of data necessary for decision-making.
 
- Clinical cases with a principal diagnosis other than valvular heart disease.
 
- Presence of bacterial endocarditis.
 
	
Primary and Secondary Outcomes	
It is considered clinically beneficial to increase the number of appropriate recommendations by 15% over the recommendations generated with general management without the support system.
 
The baseline/pre-test value is the number of appropriate recommendations based on clinical practice guidelines during conventional management (without CDSS). Inappropriate recommendations as judged by the committee of expert assessors during conventional management will also be collected.
 
The post-intervention/post-test value is the number of appropriate guideline-based recommendations after activation of the naevia medical decision support system. Inappropriate recommendations in the judgement of the committee of assessors during CDSS management will be collected.
 
To calculate the percentage increase between two values we will use the following formula:
 $\text{Percentage increase} = (\text{Post-intervention value} - \text{Baseline value}) / \text{Baseline value} \times 100$	

Dilemma Solutions S.L.	CHAPTER 06-1C	TD01-06-1C Ver.: 01 2025/03/03
	CLINICAL EVALUATION PLAN (CEP)	Page 34 of 38

Title	Clinical validation study of naevia medical, a decision support tool for valvular heart disease
	value) ×100%.
Protocol reference	TD01-06-1C-06-02 CIP_NCT06392464

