### Statistical analysis plan

The study is designed as a pre-test-post-test evaluation of a randomly assigned group, using a longitudinal repeated measures approach and retrospective validation. The clinical management of the included cases will be retrospectively evaluated by a panel of 3 experts with access to the most updated guidelines. For each case, the panel will perform the assessment at baseline (without CDSS) and repeated the assessment after the activation of the CDSS. The experts will label all the given clinical recommendations as appropriate or inappropriate and will identify the ones that are missing but relevant for clinical decision making. Finally, they will state their grade of agreement with the CDSS suggestions on a five-level Likert scale. The number and percentage of appropriate, inappropriate and missing relevant recommendations in each scenario will be considered for analysis.

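### In Table 1's two misdiagnosis rows, the 'none observed' limb cannot fail on the clinical studies described, because none is shown to put CDSS output into patient care

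*Protocol*

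**What the plan says.** Table 1 (Protocol section 11) has a row for misdiagnosis through product error and one for misdiagnosis through user error. Each sets a measure and two limbs.

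- **Measure:** "Incidence with SW System not > documented incidence with similar devices". No comparator rate or margin is given.
- **First limb:** in the product-error row, no serious complications tied to "misdiagnosis caused by product's error in the DUE are observed in the clinical studies and registries performed with the DUE"; the user-error row has matching wording. No number exposed, follow-up time or upper bound is given.
- **Second limb:** "Output from ongoing review of incidents and adverse events (if any) related to the DUE and similar devices confirms a low incidence". The word low carries no number.

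In both rows the first limb is attached to a rule that incidents do not cause serious harm, and the second to a rule that they do not often do so.

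The main study (Protocol section 14, Main clinical investigation) is a retrospective validation on 101 cases seen in 2022. The SAP says: "The clinical management of the included cases will be retrospectively evaluated", by a panel of three experts, first without and then with the CDSS. Section 14 also lists a retrospective colorectal screening cohort (69 participants) and a hypertrophic cardiomyopathy study in which experts and non-experts answered questions on cases. Two registries (168 and 991 cases) are described only as using the platform, and an ongoing rehabilitation registry is named without a size. The section 14 Overview states that "NAEVIA MEDICAL, has not been on the market before".

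**The concern.** Section 10.1 describes both misdiagnosis risks as a user acting clinically on wrong advice. A complication of that kind needs a patient whose care was influenced by the CDSS, and someone recording what happened next. In the main study, care had been given before the CDSS was switched on. No supporting study is described as having its output acted upon. A requirement that no complications be observed is then satisfied by design and says nothing about the device.

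Table 1 is the stated basis for accepting the benefit-risk ratio, section 11 says the device's own studies will support its safety profile, and section 13 anticipates high-level evidence. Read literally, the first limb would let studies with no exposed patients count as clinical evidence of safety.

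**Working it through.** The rows state no sample size, event rate or margin, so there is no figure of the plan's to reproduce. The check has two parts.

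**1. Can each source produce the event?**

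| Source (Protocol section 14) | Size | CDSS output used in care? | Events followed? |
|---|---|---|---|
| Main study | 101 | Not described; 2022 cases re-read by a panel | Not described |
| Colorectal cohort | 69 | Not described; retrospective | Not described |
| Cardiomyopathy study | 60 cases in internal validation, then case questions | Not described | Not described |
| Two registries | 168 + 991 = 1,159 | Not stated either way | Not stated |
| Rehabilitation registry | Not stated | Not stated | Not stated |

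The cardiomyopathy study shows the gap in the plan's own figures. With the CDSS, experts still gave 144 wrong answers and non-experts 208. Whatever their cause, none of these could have registered as a patient complication.

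**2. What would the limb tell us?**

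Let n be the number of exposed and followed patients and p the true rate of serious complications.

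- Probability that the limb fails: 1 − (1 − p)^n
- Exact one-sided 95% upper bound after 0 events: 1 − 0.05^(1/n); with n = 0 nothing is excluded and the bound is 100%.

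| n | p = 0.1% | p = 0.5% | p = 1% | p = 3% | Upper bound if 0 events |
|---|---|---|---|---|---|
| 0 (studies as described) | 0 | 0 | 0 | 0 | 100% |
| 101 (if all main-study cases had been exposed and followed) | 9.6% | 39.7% | 63.8% | 95.4% | 1 − 0.05^(1/101) = 2.9% |
| 1,159 (if all registry cases were exposed and followed) | 68.6% | 99.7% | >99.9% | >99.9% | 1 − 0.05^(1/1159) = 0.26% |

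The first line follows from the descriptions. The other two are illustrations: the documents do not say that any of these patients was exposed, and the values of p are assumptions.

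**The case against.** A reader might infer more: that all three incident-based safety rows, including privacy, cannot fail, and that a device giving wrong advice in every case would pass Table 1. The documents do not support that, for four reasons.

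- **Registries.** The limb covers registries as well as studies. Exposure there is undescribed, not shown to be absent, and never having been marketed does not rule it out. So the limb as a whole is not proven unfailable. This stands, and it limits the point to the studies. It does not rescue the limb, because a bound that could lie anywhere from 0.26% to 100% is not a usable criterion.
- **Privacy.** That row reads "No serious clinical complications or other effects linked to patient's privacy and data issues in the DUE are observed in the clinical studies". A data incident can occur while records are processed, without any patient receiving advice. The main study's exclusion of cases that cannot be anonymised lowers that risk but does not remove it. This stands. The privacy row also has no wording about frequent harm, so the inconsistency between the two harm rules is confined to the misdiagnosis rows.
- **Other limbs.** Each row also has incident review and a comparison with similar devices, which can fail in principle. This stands, although neither has a number, and before marketing the review must lean largely on other devices.
- **Other rows.** Table 1 separately requires fewer inappropriate and missing recommendations, and a check of whether the CDSS issues recommendations that could lead to a serious adverse event. A device that was always wrong would fail these. This stands and is the strongest reply: the benefit-risk conclusion does not rest on the first limb alone. But those rows do not make the first limb informative.

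It is also fair that Table 1 is titled as indicative, that section 7.1 already gives absence of complications to post-market surveillance, and that the two harm rules may be meant as tiers for different data sources. The table does not say so.

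**Conclusion.** The point holds for the product-error and user-error rows. On the clinical studies described, the first limb has zero probability of failing at any true rate of harm, and 0 of 0 exposed patients gives no bound. For the registries it is undetermined. The effect is confined to one limb of two rows, and other rows of Table 1 partly cover the same risk, but as written the limb would credit studies with safety evidence they cannot supply.

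This rests on the descriptions in Protocol section 14 and the SAP being complete as to exposure and follow-up. If a study or registry protocol shows that CDSS output reached treating physicians and that events were captured, those patients become a real denominator and the limb becomes informative for them.

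**What to change.** In the two misdiagnosis rows of Table 1:

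1. State that studies in which CDSS output did not reach patient care do not count towards the 'none observed' limb.
2. Apply that limb only to registry and PMS/PMCF data with documented exposure and event capture. Report events over exposed patients with an exact 95% upper bound, and set a numeric comparator or target bound. For scale, ceil(ln 0.05 / ln(1 − t)) exposed patients with no event are needed to bring the one-sided bound to t or below: 99 for 3%, 299 for 1%, 598 for 0.5%, 2,995 for 0.1%. These targets are assumptions, since the plan gives none.
3. Before marketing, rest these rows on what the main study can measure: the rates of inappropriate and of potentially harmful recommendations that Table 1 already calls for, per case and per recommendation, with 95% CIs. The SAP lists only appropriate, inappropriate and missing labels, so it needs a line adding the harm label.
4. Reconcile the rule that incidents do not cause serious harm with the rule that they do not often do so, or say which data source each governs.

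A field recording whether an inappropriate recommendation arose from product error or from user or data-entry error would help but is optional, because the documents do not show that the panel can compare inputs with source records.

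The cost is rewording two rows, one SAP line and an exposure statement for each study and registry. If the panel's labelling is already complete, the harm label may need a second look at recommendations marked inappropriate or missing. The pre-market safety claim becomes more modest.

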## **12. Benefit-risk issues relating to the specific components – use of pharmaceuticals, non-viable animal, or human tissue.**

The device under evaluation does not include pharmaceuticals, medicinal products or non-viable animal or human tissue.

## **13. Required level of clinical evidence**

As outlined previously, literature search and review shall be conducted to establish the state of the art. Literature search is also expected to yield up-to-date information concerning current alternatives and standard of care.

Taking into account the characteristics of the device and its intended purpose, it is expected that robust, published clinical data concerning similar devices shall be found and can be obtained in order to incorporate it fully into the technical documentation. Equivalence with one of these similar devices is anticipated enabling the leveraging and use of this data to establish sufficient clinical evidence. Scientific quality of the available data shall be assessed during the appraisal stage of the clinical evaluation. Appraised datasets that qualify as clinical data shall be the basis for analysis to determine if the available information provides sufficient clinical evidence.

Dilemma Solutions S.L.	CHAPTER 06-1C CLINICAL EVALUATION PLAN (CEP)	TD01-06-1C Ver.: 01 2025/03/03
		Page 31 of 38

In order to define the required level of clinical evidence, reference is taken from what is established in Appendix III of Guidance document MDCG 2020-6. Note that this guidance document refers to legacy devices (medical devices previously CE marked under Directives 93/42/EEC), thus it is only considered to establish the hierarchy of the clinical evidence. The level of clinical evidence found may be ranked (e.g., Rank 1 to Rank 12 where Rank 1 are results of high-quality clinical investigations, Rank 4 are Outcomes from studies with potential methodological flaws but where data can still be quantified and acceptably justified, and Rank 12 are Preclinical and bench testing / requirements to standards) and are likely to vary between:

- **High Level (Rank 1 to Rank 4):** Includes data sourced from clinical investigation(s) with the DUE itself or data sourced from other clinical studies with the DUE itself where the data can be quantified, and it is acceptability justified.
- **Medium Level (Rank 5, 6):** Includes data sourced from clinical investigation(s) or other clinical studies with a device demonstrated to be equivalent to the DUE.
- **Low Level (Rank 7, 8, 9):** Includes data sourced from curated complaints and vigilance data or structured, proactive PMS data pertaining to the DUE. Case reports on the DUE. Clinically relevant information pertaining to similar (but non-equivalent) devices.
- **Non-clinical (Rank 10, 11, 12):** Evaluation of the state of the art based on data from similar devices. Compliance to non-clinical elements of common specifications. Simulated use, animal or cadaver testing involving end-users. Pre-clinical and bench testing showing compliance to standards.

For this device, taking into account the device risk class, characteristics and intended purpose, it is anticipated that HIGH level clinical evidence can provide enough specific information for conformity assessment purposes.

#### **14. Clinical development plan (CDP)**

The purpose of this section is to establish a plan indicating the progression of our clinical development as referred to in Annex XIV Part A of MDR with an indication of milestones and a description of potential acceptance criteria.

Any clinical investigation envisaged shall be planned and conducted in line with regulatory and ethical requirements applicable in the country where the investigation is to be performed and in accordance with good clinical practice as set out in standard ISO 14155 (ISO/TC194 2021).

Dilemma Solutions S.L.	CHAPTER 06-1C CLINICAL EVALUATION PLAN (CEP)	TD01-06-1C Ver.: 01 2025/03/03
		Page 32 of 38

## Overview

This is the first Clinical Evaluation Plan according to the Regulation (EU) 2017/745 on medical devices, since the DUE, NAEVIA MEDICAL, has not been on the market before (2017).

## Clinical Investigations Undertaken

The following tables summarize the clinical investigations that have been placed for the DUE:

### Main clinical investigation

Title	Clinical validation study of naevia medical, a decision support tool for valvular heart disease
Registration number	ClinicalTrials.gov ID NCT06392464
Start and End	2024
Publication	Pending
Design	pre-test-post-test of a randomly assigned group, using a longitudinal repeated measures approach and retrospective validation
Duration	3 months
Centres	Instituto de Investigación Sanitaria de Santiago de Compostela (IDIS)
Sponsor	DILEMMA SOLUTIONS SL
Main objective	Demonstrate that the use of the naevia medical CDSS significantly increases appropriate recommendations based on clinical practice guidelines, and decreases the number of inappropriate recommendations received by the patient, compared to conventional management.
Device investigation under	Naevia medical
Number of participants	101

Dilemma Solutions S.L.	CHAPTER 06-1C CLINICAL EVALUATION PLAN (CEP)	TD01-06-1C Ver.: 01 2025/03/03
		Page 33 of 38

Title	Clinical validation study of naevia medical, a decision support tool for valvular heart disease	
Inclusion criteria	
Retrospective clinical retrospective cases of patients with valvular heart disease will be selected in a stratified randomised manner from among:
 
 
(i) patients presented at a medical-surgical session.
 
ii) patients from the monographic consultation of valvopathies.
 
 
Inclusion criteria:
 
 
- Clinical cases of patients randomly selected from among those presented during the year 2022 in medical-surgical session with the main diagnosis of aortic valvular stenosis, aortic insufficiency, mitral stenosis and mitral insufficiency (greater than moderate grade). Randomisation will be stratified ensuring that 50% come from the medical-surgical session.
 
- Clinical cases of patients randomly selected from clinical records of the Valvopathy Consultation seen in 2022 with the main diagnosis of aortic stenosis, aortic insufficiency, mitral stenosis and mitral insufficiency (major degree).
 
mitral regurgitation (greater than moderate grade). Randomisation will be stratified by ensuring that at least 40% of patients have aortic valve disease and 20% have mitral valve disease.
 
- Age <math>\geq 18</math> years.
 
	
Exclusion criteria	
 
- Subjects under 18 years of age.
 
- Inability to anonymise the case.
 
- Clinical cases of valvular heart disease involving complex congenital heart disease.
 
- Clinical cases that do not meet the minimum set of data necessary for decision-making.
 
- Clinical cases with a principal diagnosis other than valvular heart disease.
 
- Presence of bacterial endocarditis.
 
	
Primary and Secondary Outcomes	
It is considered clinically beneficial to increase the number of appropriate recommendations by 15% over the recommendations generated with general management without the support system.
 
The baseline/pre-test value is the number of appropriate recommendations based on clinical practice guidelines during conventional management (without CDSS). Inappropriate recommendations as judged by the committee of expert assessors during conventional management will also be collected.
 
The post-intervention/post-test value is the number of appropriate guideline-based recommendations after activation of the naevia medical decision support system. Inappropriate recommendations in the judgement of the committee of assessors during CDSS management will be collected.
 
To calculate the percentage increase between two values we will use the following formula:
 $\text{Percentage increase} = (\text{Post-intervention value} - \text{Baseline value}) / \text{Baseline value} \times 100$	

Dilemma Solutions S.L.	CHAPTER 06-1C	TD01-06-1C Ver.: 01 2025/03/03
	CLINICAL EVALUATION PLAN (CEP)	Page 34 of 38

Title	Clinical validation study of naevia medical, a decision support tool for valvular heart disease
	value) ×100%.
Protocol reference	TD01-06-1C-06-02 CIP_NCT06392464

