It is important to emphasize that naevia medical does NOT replace the physician nor does it make autonomous decisions regarding patient management; its function is limited to presenting a prioritized series of knowledge recommendations that the professional can review and choose to adopt or not. These recommendations are explainable by showing the facts that triggered the recommendation, reproducible, and supported by information referenced in bibliographic citations. In this regard, naevia medical does NOT use artificial intelligence algorithms based on case learning nor does it employ generative technologies.

The product aims to provide this support safely for the patient, without undesirable side effects or adverse events under normal conditions of use.

*[GSPR #2] The requirement in [Annex I of the MDR] to reduce risks as far as possible means the reduction of risks as far as possible without adversely affecting the benefit-risk ratio.*

Relevant clinical data are to be located concerning:

- Acceptability of the benefit-risk profile → Compatibility with a high level of protection of health and safety

The risk-benefit relationship is favourably justified when the benefits in improving the quality of care, increasing appropriate recommendations, and decreasing inappropriate ones outweigh the risks associated with the use of CDSS. This requires careful modelling of knowledge, correct implementation, constant monitoring, and continuous updating. Acceptance of the system by clinical users is crucial and must be ensured through appropriate training, support, and participation in system improvement.

Deterministic rules are widely used for problem-solving. The application of a set of clinical rules to the specific data of a patient enables the logical generation of recommendations and allows for the review of knowledge that applies to a particular case. However, it should be considered that there is intrinsic uncertainty in each decision-making problem, and the medical knowledge managed by a system has limitations.

With the objective of reducing risks the knowledge modelling and rule-making system of naevia medical facilitates semantically well-formed rules with coherent logic. The peer review process aims to ensure that the variables and propositions used have the same meaning as the texts of the recommendations they intend to model.

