Design	Observational, multicenter study for the validation of a digital clinical decision support tool (CDSS) applied to clinical cases of patients with hypertrophic cardiomyopathy.
Duration	9 months
Centres	Hospital Virgen de la Arrixaca
Sponsor	Amicus Therapeutics.
Main objective	To evaluate the degree of concordance between management decisions of experts (Standard Output) versus non-experts supported by the CDSS (non-experts+CDSS output), in patients with HCM.
Device investigation under	Naevia medical
Number of participants	4101 rules (algorithms) covering HCM and related problems (heart failure, atrial fibrillation, valvular heart disease, arterial hypertension, dyslipidaemias, diabetes, coronary syndromes) were coded in the CDSS and were evaluated in 60 cases (internal validation).
Inclusion criteria	Patients evaluated consecutively with a main diagnosis of hypertrophic cardiomyopathy in which the available clinical information is considered sufficient for the generation of diagnostic and therapeutic recommendations.
Exclusion criteria	Absence of relevant clinical information for medical decisions. Problems for case anonymization.
Primary Outcomes	External validation phase 1: For each question (n=42), the experts (n=10) provided a total of 56 answers (28 with and 28 without CDSS) and non-experts (n=9) provided 62 answers (31 with and 31 without CDSS), to sum a total of 2184 individual questions (42 per case in 26 cases evaluated twice) and 4956 answers (including 248 answers that were considered the references, and 4708 answers to be evaluated). In experts, the number of right answers improved with CDSS from 1020 to 1032 (1.1%) and the number of wrong answers decreased from 156 to 144 (7.6%) (p=0.46). In non-experts, the number of right answers improved from 1074 to 1094

Dilemma Solutions S.L.	CHAPTER 06-1C CLINICAL EVALUATION PLAN (CEP)	TD01-06-1C Ver.: 01 2025/03/03
		Page 36 of 38

Title	Development and pre-clinical evaluation of an advanced decision support system for hypertrophic cardiomyopathy clinical management

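### The main objective claims fewer inappropriate recommendations reaching patients, but the study scores past cases and counts what is generated, with no step in which a clinician accepts or rejects CDSS output

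*Protocol*

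**What the plan says.** In the Protocol, section 14, table for the main clinical investigation, the objective is that use of the CDSS raises appropriate recommendations and "decreases the number of inappropriate recommendations received by the patient, compared to conventional management". The same table gives the design as "pre-test-post-test of a randomly assigned group, using a longitudinal repeated measures approach and retrospective validation". One case source reads "Clinical cases of patients randomly selected from among those presented during the year 2022 in medical-surgical session"; the other is the valve clinic's records for the same year. The study itself is dated 2024.

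The outcome row of that table defines the post-test value as the number of appropriate guideline-based recommendations "after activation of the naevia medical decision support system". Inappropriate ones are collected under management with the CDSS, a term it does not define.

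On intended use, section 4 (under GSPR #1) says of the device that "its function is limited to presenting a prioritized series of knowledge recommendations that the professional can review and choose to adopt or not".

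The SAP says "The clinical management of the included cases will be retrospectively evaluated by a panel of 3 experts". The panel assesses each case without the CDSS and again after activation. The analysed variable, under the SAP heading on amount and quality of recommendations, is the count generated per patient, compared by the Wilcoxon signed-rank test.

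**The concern.** The objective is about what reaches the patient; the analysed variable is what is produced for a case record. Between the two lies the clinician's decision, which the plan itself describes as a choice to adopt or not. If that decision is not observed, the study cannot show that using the tool changes what patients receive, however large the difference in counts.

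This matters because section 7.1 and Table 1 of the Protocol rest the benefit-risk case on this study: a threefold rise in appropriate recommendations and a reduction in inappropriate and missing ones. A conclusion carried there in terms of patient receipt would go beyond the evidence.

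**Working it through.** The plan gives no figure for this point, so the check is mainly a comparison of passages. Two illustrations on assumed inputs follow.

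**1. Objective against measurement.**
- Claimed (objective row, section 14): a change in what patients receive when the CDSS is used.
- Cases (inclusion row): managed in 2022. Activation takes place within the later study, after the recorded care was given.
- Measured (SAP): counts generated per patient.
- Link needed: acceptance or rejection by an intended user, whom section 6 defines as a doctor or resident familiar with the tool. Neither document describes such a step before counting.

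Receipt by patients is therefore not observed on the CDSS side of the comparison.

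**2. What the post-test set could be.** The two documents allow three readings.
- *CDSS output alone.* The count describes the software's suggestions before any adoption decision.
- *Chart plus CDSS.* Let B be the inappropriate items in the chart and N the new inappropriate items from the CDSS, with N at least 0. If chart items and their labels carry over unchanged, post-test count = B + N, and the change is N, which cannot be negative. The appropriate count likewise cannot fall, though it need not rise.
- *The panel's own assessment with CDSS access.* Judgement acts on both sets and either count can move in either direction. But the panel is three experts with current guidelines, not the treating clinicians, and again no patient received the result.

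None of the three measures what patients received.

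**3. Illustration: generated against received (adoption rate a is assumed).** Let R be the generated post-test to baseline ratio of appropriate recommendations.
- CDSS output alone, counting only adopted suggestions as received: ratio received = R × a.
- Chart plus CDSS, all chart items kept and additions adopted at rate a: ratio received = 1 + (R − 1) × a.

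The plan's two success thresholds supply R: 3 (section 7.1, Table 1) and 1.15 (outcome row).

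| a | R = 3, CDSS alone | R = 3, chart plus CDSS | R = 1.15, CDSS alone | R = 1.15, chart plus CDSS |
|---|---|---|---|---|
| 25% | 0.75 | 1.50 | 0.287 | 1.038 |
| 50% | 1.50 | 2.00 | 0.575 | 1.075 |
| 75% | 2.25 | 2.50 | 0.862 | 1.112 |
| 100% | 3.00 | 3.00 | 1.15 | 1.15 |

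At R = 1.15, CDSS output alone needs a = 1/1.15 = 87% adoption merely to equal baseline.

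**4. Illustration: does the choice of set matter for the test?** Simulation of 101 pairs (the plan's number), 1,000 replicates, two-sided Wilcoxon at an assumed 0.05. Inappropriate counts were assumed independent Poisson with a chart mean of 0.5. Share of replicates with a significant decrease:

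| Assumed CDSS mean | CDSS alone | Chart plus CDSS | Half of CDSS output adopted, no chart items kept |
|---|---|---|---|
| 0.3 | 61.4% | 0% | 99.7% |
| 0.5 | 2.4% | 0% | 83.6% |
| 1.0 | 0% | 0% | 2.8% |

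Under chart plus CDSS, every replicate gave a significant increase. The means are not from the documents; the table shows only that the definition can decide the result.

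**The case against.** **The phrase occurs once, in a summary row.** The SAP already counts recommendations generated, and the safety row of Table 1 already speaks of what the device issues. This stands as to scope: the remedy is mainly one sentence. But that sentence is the main objective, and it governs what the study may be said to show.

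**A separate investigation plan may settle the post-test set.** The table cites one (TD01-06-1C-06-02) that is not among the documents reviewed. This stands: one can say only that the Protocol and SAP supplied do not define the set.

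**A reader might infer that the study compares clinicians' filtered decisions with raw, unfiltered CDSS output.** That is a natural reading, since the Likert rating is of CDSS suggestions, but it is not stated. The SAP also allows the panel to assess without and then with the tool, so that judgement acts on both sets.

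**A reader might infer that a rise in appropriate recommendations is guaranteed and a fall in inappropriate ones impossible.** The second half holds only if chart items carry over unchanged, which no passage says. Even then the appropriate count merely cannot fall.

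**A reader might use the supporting cardiomyopathy study to size the gap between generated and used.** Right answers rose from 1020 to 1032 in experts (12/1020 = 1.18%) and from 1074 to 1094 in non-experts (20/1074 = 1.86%). That study reports no count of generated recommendations, so it cannot show such a gap. It was also near its ceiling: with 156 and 228 wrong answers at baseline, the largest possible rises were 156/1020 = 15.3% and 228/1074 = 21.2%.

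**Imposing one post-test definition now could redefine the primary outcome after scoring.** Section 7.1 and Table 1 already report panel agreement in the past tense. This stands, and the fix below imposes none.

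**Conclusion.** The point holds for the objective and for conclusions drawn from it. A retrospective scoring of 2022 cases, with counts of recommendations generated and no described acceptance step, cannot support a conclusion about what patients receive. This rests on the text and on no numerical assumption.

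The gap cannot be sized from the documents, which give neither adoption rates nor baseline counts. The adoption and simulation figures are illustrations only.

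The undefined post-test set is a secondary matter. On its own it is closer to missing detail, but it must be stated before any reduction in inappropriate recommendations is claimed. The documents do not show that the set is unfiltered CDSS output, nor that the study is bound to fail or succeed on either objective.

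**What to change.** 1. In the main objective (Protocol, section 14), delete the reference to receipt by the patient. Restate the objective as the number of appropriate, inappropriate and missing recommendations generated with the CDSS, compared with those recorded in conventional management. Word any conclusion taken from it to the acceptance criteria in section 7.1 and Table 1 in the same terms.
2. In the Protocol and the SAP, state which post-test set was actually scored: CDSS output alone, chart plus CDSS, or the panel's assessment with CDSS access. Make this consistent with the separate investigation plan, and disclose it if the definition was fixed after scoring.
3. If chart items were carried over unchanged, make no claim of a reduction in inappropriate recommendations.

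The cost is wording in two documents and a more modest claim. No new cases are needed.
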